- C. **Randomization.** Participants will be randomized to one of three parallel arms using a SAS computer program. Block randomization will be implemented to ensure balance between the three groups. Randomization will be stratified by according to whether the participants are eligible for (and consented to) muscle biopsy.
- D. **Rationale for focus on walking exercise.** Walking exercise is the only form of exercise that consistently improves walking performance in PAD and is the only exercise currently recommended by practice guidelines for PAD (1,2,27,64).

3.2 Criteria.

Inclusion and exclusion criteria. All participants will have PAD. PAD will be defined as follows. First, an ABI ≤ 0.90 at the baseline study visit is a well-accepted standard for the diagnosis of PAD and will be an inclusion criterion (59-62). Second, people with an ABI of >0.90 and ≤ 1.00 who experience a 20% ankle systolic pressure drop after the heel-rise test will also be included. Third, potential participants with an ABI > 0.90 who have vascular lab evidence of PAD* or angiographic evidence of PAD** who have ischemic symptoms during the six-minute walk and/or treadmill exercise stress test will be eligible. In addition to meeting a criterion for PAD, all participants must be symptomatic, defined by one of the following criteria:; a) ischemic leg symptoms (primarily assessed with the San Diego Claudication

PROTOCOL TITLE: Low InTensity Exercise intervention in PAD: The LITE Trial

Questionnaire); b) report ischemic leg symptoms at the end of the six-minute walk; c) report ischemic leg symptoms at the end of the baseline treadmill stress test; d) walking impairment questionnaire results, e) interview with the potential participant about the presence and nature of leg symptoms during walking activity. Exclusion criteria are listed in Table 3.

* If the only criterion by which a participant is eligible to participate is a toe pressure, the toe pressure must be < 70 or the toe brachial index ratio must be < 0.60 if asymptomatic or < 0.70 if symptomatic.

** Angiographic criteria of PAD consist of a stenosis of 70% or greater in a lower extremity artery.

Table 3. Summary of exclusion criteria and justification for each criterion.

List of specific exclusion criteria	Justification for exclusion criteria
1. Above or below knee amputation, critical limb ischemia, wheelchair confinement, or foot ulcer.	1. Inability to fully participate in the intervention.

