
In addition, in a subset of participants we will obtain a muscle biopsy on the left and the right legs, respectively. These bilateral biopsies could be obtained at baseline, at 12-month follow-up, or both time points. The first biopsy will be performed as per our current procedures. The second biopsy will be performed seven days later when the participant returns for their incision site checks. It will be necessary for these individuals to remain off of their anti-platelet therapy for 14 days. Physician approval will be required. If the participant prefers to schedule the second biopsy at a later date (i.e. more than seven days after the initial biopsy), that will also be acceptable. In this case, anti-platelet

PROTOCOL TITLE: Low InTensity Exercise intervention in PAD: The LITE Trial

therapy will be held seven days prior to the contra-lateral biopsy. Participants will receive \$100 for their time and effort for each biopsy performed.

T. Qualitative measures. To achieve our Exploratory Aim, we will perform digitally recorded qualitative interviews among participants in the low and high exercise intensity interventions, respectively. We will assess participants overall perceptions of the exercise intervention and participant-identified facilitators and barriers to exercise behavior that is consistent with the study goals. Interviews will be performed under the direction of [name], a nationally-recognized expert in qualitative research. Prior work shows that theoretical saturation, or the point of redundancy at which no new themes emerge, often occurs in interview studies within the first 12 interviews; basic elements for themes may be present as early as six interviews (94). We will interview 15-20 randomly selected participants in each of the low- and high-intensity groups. Following transcription, responses to these open-ended items will be independently coded by the qualitative interviewers and [name] using content and constant comparative analysis (95-97).

U. Other measures. As in our previous trials, patient report will be used to document comorbidities. Patient report is highly correlated with comorbid disease measured with medical record review (98-101). Participants are asked to bring their medication bottles to each visit to assess medication use.

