C. **Minimizing risks related to muscle biopsy.** The muscle biopsy procedure will be performed by [name] who has more than 30 years of experience performing these muscle biopsies, primarily as part of his clinical practice as a Board-Certified Neurologist. As in our pilot study, completed in preparation for this proposal, the muscle biopsy procedures will be performed under sterile conditions using sterile technique. Local anesthesia will be obtained using subcutaneous lidocaine. All participants will be provided with written and verbal instructions about wound care and will be advised to contact [name] immediately if any signs of wound infection occur. All participants will return for a one-week follow-up check of their incision site.

Many PAD participants take anti-platelet therapy to prevent cardiac and cerebrovascular events. If potential participants are taking anti-platelet therapy, they will be asked to either hold their anti-platelet therapy (if they are taking 81 mgs of aspirin or less per day) or switch to a low dose (81 mgs) of aspirin therapy (if they are taking clopidogrel or an equivalent medication or > 81 mgs of daily aspirin at study entry) during the seven days leading up to the muscle biopsy procedure. Participants who are taking warfarin or other anti-coagulant therapy will be excluded from the muscle biopsy procedure.

D. **Minimizing risk related to baseline and follow-up testing.** All study coordinators undergo baseline training and are certified by [name] before beginning data collection. Training and certification involves ensuring that coordinators are trained in methods to help minimize falls. [name] re-certifies coordinators every six months to ensure continued adherence to study protocol. Those who are not adhering to protocol undergo additional training followed by re-certification.

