Third, exercise may be associated with muscle fatigue or soreness. This typically resolves with rest.

Fourth, it is possible that walking may contribute to foot sores when shoes are poorly fitting. Additionally, walking may worsen or slow healing of foot sores or ulcers in PAD.

Fifth, risks associated with baseline and follow-up testing include loss of balance and falling during the walking tests, chair rises, and standing balance testing. However, the research assistant who will collect these data has been trained to prevent falling. The risk of falling is less than 1 in 200. Falling during these tests may be associated with fracture. The risk of a fracture secondary to a fall during the walking tests is less than 1 in 5,000.

B. Risks associated with the muscle biopsy. The muscle biopsy is associated with several potential risks. These include discomfort during the muscle biopsy procedure, scarring from the muscle biopsy skin incision, bleeding, and infection. Potential participants who are asked to hold or reduce their anti-platelet therapy or anti-coagulation therapy during the week leading up to the muscle biopsy procedure may experience a cardiovascular event related to the temporary reduction or discontinuation of the anti-platelet or anti-coagulant therapy.

To minimize risk, all participants undergoing muscle biopsy will receive a written hand-out regarding signs to watch for of wound infection after the muscle biopsy. They will also be verbally instructed in this. The participant will be instructed to call [name] immediately if any signs of infection occur. In addition, permission from the participant's primary care physician will be required before switching participants on anti-coagulant therapy to low-dose aspirin therapy for the seven days prior to the procedure. If the potential participant's primary care physician does not provide permission for switching to low-dose aspirin for patients taking anti-coagulant therapy, the potential participant will not be eligible for the study. However, based on our pilot study, we anticipate that the number of these exclusions will be very small.

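### Section 9.2 bars participants on an anticoagulant from the muscle biopsy, while Section 14.1 describes interrupting the anticoagulant so that the biopsy can go ahead

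*Combined protocol and SAP*

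**What the plan says.** Three parts of the protocol bear on this point.

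- **Section 9.2, risk-minimisation list, item C (muscle biopsy).** For anti-platelet drugs there is a rule for the seven days before the procedure. Those on 81 mg of aspirin or less hold it. Others are to "switch to a low dose (81 mgs) of aspirin therapy (if they are taking clopidogrel or an equivalent medication", and the same applies to those on a higher aspirin dose. For anticoagulants the rule is a plain exclusion: "Participants who are taking warfarin or other anti-coagulant therapy will be excluded from the muscle biopsy procedure".
- **Section 14.1.B (risks of the muscle biopsy).** The cardiovascular-event warning covers potential participants "who are asked to hold or reduce their anti-platelet therapy or anti-coagulation therapy during the week leading up to the muscle biopsy procedure". Permission from the primary care physician "will be required before switching participants on anti-coagulant therapy to low-dose aspirin therapy for the seven days prior to the procedure". If that physician "does not provide permission for switching to low-dose aspirin for patients taking anti-coagulant therapy, the potential participant will not be eligible for the study". On the basis of the pilot study, "we anticipate that the number of these exclusions will be very small".
- **Sections 3.1.C and 3.2.** Randomization is stratified by whether the participant is eligible for, and has consented to, the biopsy. On eligibility for the trial, Section 3.2 says "Exclusion criteria are listed in Table 3". None of that table's ten criteria concerns anticoagulant use or a physician's refusal.

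Section 9.2.S adds a rule for bilateral biopsies only: "It will be necessary for these individuals to remain off of their anti-platelet therapy for 14 days. Physician approval will be required".

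**The concern.** One section gives an unconditional exclusion and the other a conditional permission for the same people. Both are current text, and neither says which governs. The biopsy is done for research (Secondary Aim #6), and the protocol itself names a cardiovascular event as a risk of reducing these drugs. Staff working from Section 14.1.B could replace a participant's anticoagulant with aspirin for a week, for a procedure that Section 9.2 forbids that participant to have.

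The refusal sentence raises a second question. If it means the whole trial, a person could be turned away because a physician would not allow a drug change that is needed only for an optional component.

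**Working it through.** The plan states no figure on this point, so the check sets the texts side by side, case by case.

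| Participant | Section 9.2, item C | Section 14.1.B | Consistent? |
|---|---|---|---|
| On an anticoagulant, physician agrees to a switch | No biopsy; no switch route given | Biopsy after seven days on low-dose aspirin | No |
| On an anticoagulant, physician refuses | No biopsy; silent on trial entry | Not eligible for the study | Depends on what the study means |
| On an anti-platelet drug only | Hold, or switch to 81 mg aspirin, for seven days; no permission step stated | Warning applies; permission sentences do not name this class | Incomplete, not contradictory |

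**First row.** The conflict does not depend on what the study means, because it concerns the biopsy itself. It would go away only if anticoagulant in the permission sentences were loose wording for anti-platelet. Even then, the warning in the preceding paragraph of Section 14.1.B names the two classes separately and still speaks of reducing anticoagulation, which Section 9.2 gives no reason to do.

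**Second row.** Section 3.1.C has a stratum for people who are not eligible for biopsy or have not consented to it, so such people are expected to be randomized. A trial-wide exclusion on refusal does not fit that. An exclusion from the biopsy alone does.

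**Third row.** Section 9.2.S requires physician approval for bilateral biopsies, where anti-platelet therapy stops for 14 days. For an ordinary single biopsy, the only permission step is the one in Section 14.1.B, and it is worded for the class that Section 9.2 bars.

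**Size.** The two rules differ in who is biopsied only for participants on an anticoagulant whose physician would agree. That number is (biopsy candidates) × (share on an anticoagulant) × (share whose physician agrees), and the documents give neither share. The sponsor's expectation of very few exclusions concerns refusals, so it does not supply the missing figure.

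**The case against.** The strongest reply is that Section 14.1.B is only loosely worded. Its seven-day switch to low-dose aspirin matches Section 9.2's clopidogrel rule in drug and timing, so anticoagulant may have been written for anti-platelet. The refusal sentence stands under a heading about the biopsy, so the study may mean the biopsy component. Both readings are plausible. If both are adopted, most of the conflict disappears, but the text settles neither. If only the first is adopted, the refusal rule would reach anti-platelet users, whom Section 9.2 describes as many.

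A reader might infer a hidden trial exclusion from its absence in Table 3. The documents do not support that inference. The table is titled a summary, and other limits stand outside it: Section 3.3 excludes vulnerable populations, and Section 28.0 excludes people who do not speak English. The stratification in Section 3.1.C is the better evidence, and it applies only if the study means the trial.

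A reader might also try to size the problem by assuming a prevalence of anticoagulant use and asking whether 50 biopsies per arm remain attainable. That would measure the effect of the exclusion already in Section 9.2, not the difference between the two rules.

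It is also fair to say that the practical effect may be small. Section 9.2 is the procedural text and gives the safer rule. Section 9.1 already reports a trial finding, so screening may be over.

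**Conclusion.** The point holds as an internal contradiction on a safety rule. Read literally, Sections 9.2 and 14.1.B give opposite instructions for participants on an anticoagulant. The conflict over trial eligibility is conditional: it exists unless the study in Section 14.1.B means only the biopsy component.

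The number of participants affected is unknown. The primary analysis of six-minute walk distance is not affected; the only analysis touched is the biopsy comparison in Secondary Aim #6. Nothing in the documents shows that anyone had an anticoagulant interrupted or was refused entry, and the wording alone should not be taken to imply it. The matter deserves correction because the repair is simple and the risk falls on participants.

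**What to change.** Amend Section 14.1.B to match Section 9.2:

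1. Participants on warfarin or another anticoagulant are not biopsied and are not asked to hold, reduce or switch the drug for the study. They remain eligible for the main trial in the non-biopsy stratum.
2. In the refusal sentence, replace ineligibility for the study with ineligibility for the muscle biopsy.
3. Keep the cardiovascular-event warning, reworded to apply to the anti-platelet hold or switch.

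Optional: if the permission sentence was meant for anti-platelet drugs, say so in both sections, with refusal meaning no biopsy only. Against Section 9.2 as written this is an added step, and it could cost some biopsies because anti-platelet use is common in this population.

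If the biopsies are complete, report which rule was applied, and whether anyone was biopsied after anticoagulant interruption or refused trial entry.

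The cost is a wording amendment and a check of the screening instructions. Relative to Section 9.2, items 1 to 3 lose no biopsies. Relative to Section 14.1.B, they lose for Secondary Aim #6 those anticoagulated participants whose physician would have agreed.

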10.0 Data and Specimen Banking

10.1 *Storage of specimens.*

Blood specimens for long-term storage will be stored in a freezer belonging to [name] research program at Northwestern University, in the freezer farm in the basement of Olson Pavilion.

Specimens will be stored for up to 70 years, after which they will be destroyed.

10.2 *Data to be stored or associated with each specimen.*

Specimens will be coded; meaning that a key will exist that can link the codes back to the direct subject identifiers. Each participant will be assigned a unique study ID number that can be traced back to the study participant. The blood samples that are maintained in long-term storage will be labeled with this unique identifier and the date and time of the blood collection.

10.3 *Procedures to release data or specimens.*

PROTOCOL TITLE: Low InTensity Exercise intervention in PAD: The LITE Trial

Only [name] has control over release of study data or specimens. Any investigators seeking to analyze blood specimens must contact [name] for permission. Each request, if it occurs, will be considered on a case-by-case basis. [name] will obtain IRB approval prior to releasing any blood specimens for analysis, other than those tests specifically named in this application.

11.0 Data and Specimen Management

11.1 Data analysis plan.

- A. **Data management.** We will use data management methods in place for our ongoing NHBLI-funded PAD studies. Data from baseline and follow-up study visits are acquired on paper forms and processed using the Teleform system by Cardiff Software. We have successfully used this system for over 8,000 patient visits in our previous and ongoing studies. Data are backed-up on multiple hard drives and copied to CDROM for secure off-site storage.
- B. **Data Safety Monitoring Board (DSMB).** We have identified nationally recognized experts to serve on the DSMB.

Statistical Analyses. Analyses will be performed according to the intention to treat principle. Data will be analyzed according to each participant's originally assigned group, irrespective of whether the participant adheres to his/her assignment. Prior to analyses, the distributions of the variables (changes) will be examined and necessary transformations will be performed. The balance of socio-demographic factors and prognostic factors (such as age, sex, race, ABI, comorbidities, and relevant medication use) will be compared between the three groups using ANOVA or chi-square tests. If there is any indication of major imbalance, proper analysis of covariance adjustments will be performed in data analyses.

NOTE: The original plan to use two sample two-tailed t-tests was changed to a mixed model for repeated measures analysis on 8/27/2020 prior to analyzing any data. This change was made because as of 8/27/202, investigators are projecting an approximately 16% loss to follow-up rate at 52 week follow-up. The mixed model for repeated measures will be used to adjust for missing data.

For our Primary Aim, we will use mixed model for repeated measures (MMRM) analysis to compare changes in six-minute walk performance at 52-week follow-up between the low vs. the high-intensity exercise group and between the low-intensity exercise group vs. the control group, respectively. To this end, the 26-week and 52-week changes of six-minute walk from baseline are treated as correlated outcomes, and independent variables include visit (26-week and 52 week), treatment (low-intensity, high-intensity, control), visit/treatment interactions and baseline six-minute walk performance. Unstructured variance-covariance matrix will be used to model the within-person correlations. In addition, we will also adjust for potentially imbalanced baseline confounders such as age, sex and baseline six-minute walk performance. When there is evidence that the normality assumption for the distribution of measures of interest is severely violated, we will perform Wilcoxon rank-sum test for the comparison. The nonparametric adjustment for the imbalance in mean difference of baseline covariates will be employed, when needed.

PROTOCOL TITLE: Low InTensity Exercise intervention in PAD: The LITE Trial

For Secondary Aim #1, we will use MMRM analysis to compare changes in six-minute walk, physical activity, and SF-36 PF and WIQ distance and speed scores at 26-week follow-up between the low- and high-intensity exercise groups and between the low-intensity exercise and control group, respectively.

For our Secondary Aim #2, we will use MMRM analysis to compare changes in maximal treadmill walking time, physical activity, and SF-36 PF and WIQ distance and speed scores at 52-week follow-up between the low- and high-intensity exercise groups and between the low-intensity exercise and control groups, respectively.

For our Secondary Aim #3, we will use normal approximation for binomial distribution to compare the proportion of participants who achieve adherence (as defined in section C18) between the low vs. high intensity exercise groups. We will also use logistic regression to compare the adherence rate between these two groups, adjusting for potentially imbalanced baseline confounders such as age, sex, and baseline six-minute walk performance. We will also use two sample two-tailed t-tests to compare adherence to the exercise intervention overall and at the prescribed intensity between the high vs. low intensity groups at 52-week follow-up.

For our Secondary Aim #4, we will use MMRM analysis to compare changes in six-minute walk distance, physical activity, and SF-36 PF and WIQ distance and speed scores at 26-week follow-up between the high-intensity exercise and control groups.

For our Secondary Aim #5, we will use MMRM analysis to compare changes in six-minute walk distance, maximum treadmill walking time, physical activity, and SF-36 PF and WIQ distance and speed scores at 52 week follow up between high intensity exercise and control groups.

For our Secondary Aim #6, we will use two sample two-tailed t-tests to compare changes in COX, citrate synthase, and mitochondrial DNA at 52-week follow-up between the low intensity vs. the high-intensity exercise group and between the low-intensity exercise and control groups. We will also compare change in nitrotyrosine muscle measurements between the high-intensity exercise and the control groups. We will repeat these comparisons for the participants who adhere to their prescribed exercise intensity, measured by the ActiGraph.

For our Exploratory Aim #1, we will use two sample two-tailed test compare patients' perception to exercise at 52-week follow-up between high and low-intensity groups. For our Exploratory Aim #2, we will evaluate the effect of modified combo intervention (weight loss + LITE home-based exercise) on six-minute walk distance at approximately 12 week follow-up. This pilot study was completed in 2018.

The significance level for the Primary Aim will be 0.05/2 to adjust for two comparisons between low-intensity and high-intensity arms and between low-intensity and control arms.

The significance level will be 0.05 for all secondary aims. Furthermore, Secondary Aims #4 and #5 were pre-specified but added after the LITE Trial was underway in response to two negative trials of home-based exercise in patients with PAD demonstrating that a high-intensity walking exercise program did not improve six-minute walk or other outcomes in people with PAD (5, 6).

PROTOCOL TITLE: Low InTensity Exercise intervention in PAD: The LITE Trial

Missing data occur when participants are lost to follow-up. First, we will make every effort to ensure that participants return for the 52-week follow-up. We will use proxies to help us locate participants we are unable to reach and we will mail reminder letters when participants are not responsive to telephone calls. We will encourage participants who do not adhere to their assigned groups to return for the 52-week follow-up by providing transportation and monetary incentives. Thus, we anticipate that the proportion of participants without 52-week follow-up data will be small. Second, MMRM analysis is valid under the missing at random assumption. In case the proportion of missing data at 52-week follow-up is not small (>25%), we will additionally employ the multiple imputation approach to account for missing data as sensitivity analysis. If there is evidence for the possibility of missing not at random, we will perform additional analyses using pattern-mixture and shared-parameter models (105).

11.2 Power analysis.

Power estimates. For all primary and secondary aims, we anticipate a 15% drop-out rate at 52-week follow-up, based on 12-month follow-up rates in our GOALS and SILC trials (52,55). We will randomize 305 participants. Of these, 120 will be randomized to the low-intensity intervention, 120 will be randomized to the high-intensity exercise intervention, and 65 will be randomized to the control group. We will enroll more participants in each exercise group than the attention control group because we anticipate that the effect size of the low vs. high intensity exercise comparison will be lower than the effect size of the low intensity vs. the control group. For our Primary Specific Aim, we will have 80% power to detect a minimum difference of 0.43 standard deviations (SD) between the low intensity vs. high intensity exercise groups and a difference of 0.52 SD between the low-intensity and the attention control groups, in change of six-minute walk distance at 52-week follow-up, using two-sided two-sample t-tests **with a significance of 0.025 to adjust for the two comparisons.** Low intensity exercise will be considered effective if either comparison (i.e. with high intensity exercise or with the attention control group) is statistically significant. The SD of the change in six-minute walk in our GOALS and SILC trials was approximately 60 meters. Therefore, our sample size allows us to detect a difference in change in six-minute walk of 26 meters and 31 meters, respectively, between the low vs. high intensity groups and between the low intensity and control groups. Prior studies have defined clinically meaningful changes in the six-minute walk as 30 meters (small meaningful change) and 50 meters (large meaningful change) (102,103). Thus, our power should be adequate to detect a clinically meaningful difference. For our Secondary Aim #1, we will have 80% power to detect a difference of 0.39 SD between the high vs. low intensity exercise interventions and a difference of 0.47 SD between the low-intensity intervention vs. control group, respectively, in changes of six-minute walk, physical activity, WIQ scores, and SF-36 scores at 26 –week follow-up using two-sided two-sample t-tests with a significance of 0.05. For our Secondary Aim #2, we will have 80% power to detect a difference of 0.39 SD between the high vs. low intensity exercise interventions and a difference of 0.47 SD between the low-intensity intervention vs. control group, respectively, in changes of maximal treadmill walking time, physical activity, and WIQ and SF-36 scores at 52-week follow-up, using two-sided two-sample t-tests with a significance level of 0.05. In our SILC trial, the observed differences between the intervention and control groups are 0.61 SD, 0.59 SD and 0.61 SD in changes of maximal treadmill walking time, WIQ distance, and SF-36 physical functioning scores, respectively (52). In a study by Gardner et al of supervised exercise in participants with PAD (73), the observed improvement in physical activity

PROTOCOL TITLE: Low InTensity Exercise intervention in PAD: The LITE Trial

level as measured by accelerometer in the exercise group was more than 0.86 SD greater than that for the control group. Thus we should have adequate power to detect similar effect sizes. For our Secondary Aim #3, we will compare rates of ActiGraph-measured adherence to the prescribed exercise intervention (five exercise sessions per week for 45 minutes of walking exercise per session) between the low vs. high intensity exercise groups. Adherence will be defined as achieving at least 80% of the prescribed exercise intervention (see section C18). Based on the home-based component of our SILC trial, we expect the adherence rate in the high intensity exercise group will be about 30%. Our sample size provides 80% power to detect a minimum difference of 19% in the proportion of adherence between the low intensity and high intensity groups, based on the two-sided Z test with pooled variance using normal approximation for binomial distribution with a significance level of 0.05. For our Secondary Aims #4 and #5, we will have 80% power to detect a difference of 0.52 SD between the high-intensity intervention vs. control groups, in changes of six-minute walk distance, physical activity, and WIQ and SF-36 scores at 26-week and at 52-week follow-up, and in change of maximal treadmill walking time at 52-week follow-up, using two-sided two-sample t-tests with a **significance level of 0.05**. Therefore, we have adequate power for detecting differences similar to those observed in SILC trial. For our Secondary Aim #6, we will randomly select 50 participants from each of the three study groups. We will have 80% power to detect a difference of 0.61 SD between the low vs. high intensity exercise interventions, between the low-intensity exercise intervention and the control group, and between the high-intensity exercise intervention group vs. control group, respectively, in changes of citrate synthase, COX, and mitochondrial DNA at 52-week follow-up, using two-sided two-sample t-tests with a significance level of 0.05. In a randomized trial, Timmers et al reported observed differences in citrate synthase, COX, and mitochondrial DNA of 3.17 SD, 2.12 SD, and 0.75 SD, respectively, between a treatment and control group (104). Thus we should have adequate power.

11.3 Steps to secure data to maintain confidentiality during storage, use, and transmission.

First, all research assistants must complete training in protection of subject privacy and prevention of disclosure of identifying information.

Second, all data collection forms are maintained in a secure office space.

Third, our study databases are maintained in locked computer files or on secure hard-drives that are password protected; to which only authorized staff have access. [name] or a study manager must provide permission for programmers and research assistants to access study databases.

Fourth, a study identification number will be assigned to each participant. This identification number will be used to label blood specimens, for example. In addition, most pages of our data collection forms will have only the study identification number listed (and not the participant's name, for example).

11.4 Describe any procedures that will be used for quality control of collected data.

Quality Control. As in our prior studies, health interviewers will be trained by a senior coordinator and certified by [name] in each component of data collection, using a

PROTOCOL TITLE: Low InTensity Exercise intervention in PAD: The LITE Trial

detailed checklist developed for this trial. Health interviewers are rigorously evaluated for adherence to protocol, prior to beginning data collection and every six months after initial certification.

